9.1.2 Inclusion and Exclusion Criteria

9.1.2.1 Ivacaftor Cohort

Inclusion Criteria

1. Patients with CF in the CF Trust or the CF Foundation patient registries
2. Patients treated with ivacaftor

Exclusion Criterion

1. Participation in an interventional study during the analysis period (if available)

9.1.2.2 Comparator Cohort

Inclusion Criteria

1. Patients with CF in the CF Trust or the CF Foundation patient registries

2. Patients with no evidence of ivacaftor exposure (current or past)
3. Patients matched to patients in the Ivacaftor Cohort on age group, *CFTR* genotype class, and sex (see Section 9.2.4 for matching criteria)

Exclusion Criterion

1. Participation in an interventional study during the analysis period (if available)

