9.1.1 Study Population

The Ivacaftor Cohort will include all patients who have been treated with ivacaftor and are enrolled in the CF Trust or CF Foundation patient registries. The Comparator Cohort will include patients who have never been exposed to ivacaftor and are matched on age group, *CFTR* genotype class, and sex (see Section 9.2.4) to patients in the Ivacaftor Cohort.

The Ivacaftor Pregnancy Study Cohort will include all female patients who have ivacaftor exposure in the analysis year and are enrolled in the CF Trust or CF Foundation patient registries. The Comparator Pregnancy Study Cohort will include female patients who have never been exposed to ivacaftor and are matched on *CFTR* genotype class to patients in the Ivacaftor Pregnancy Study Cohort (see Section 9.2.4).

The Comparator and Comparator Pregnancy Study Cohorts will be identified for each registry's Ivacaftor and Ivacaftor Pregnancy Study Cohorts, respectively, at a ratio of m:1, where m is the maximum number of matches available.

The Historical Cohort will include patients who have the *G551D-CFTR* mutation, were enrolled in the patient registries before ivacaftor was available in clinical studies and commercially in the US and the UK (i.e., 2008), and were never exposed to ivacaftor.

The Drug Utilisation Cohort will include all patients who have ever been treated with ivacaftor.

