9.2.5 Other Matching Considerations

Given the limited size of the CF population, the Comparator and Comparator Pregnancy Cohorts will not be matched for other measures of disease severity (e.g., percent predicted FEV₁, *Pseudomonas aeruginosa* infection) due to concerns about availability of adequate patients for matching. However, measures of disease severity will be included as stratification variables and as covariates for adjustment, as necessary.

The Historical Cohort will include patients with a *G551D-CFTR* mutation who were in the patient registries in 2008. These patients were chosen because they represent the best match to ivacaftor-treated patients in 2012 and later because they match the indicated patient population based on the approved product labelling. The Historical Cohort will include patients of all ages and will be stratified to identify outcomes for patients younger than 6 years of age (for the potential off-label population). The year 2008 was chosen because starting in 2009, ivacaftor clinical studies were actively enrolling in the UK and US. A 1-year window was selected to match the window for safety outcome analysis in the Ivacaftor and Comparator Cohorts. The Historical Cohort will be analysed once for Objectives 1 and 2 for all stratification variables. If additional analyses are identified during the conduct of the study, the Historical Cohort will be available for analysis.

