9.2.6 Annual Reporting

To meet the study objectives, data for outcomes will be analysed separately for each registry for 5 years. All enrolled patients exposed to ivacaftor will be included in the Ivacaftor Cohort, and patients not exposed to ivacaftor and matched for age group, *CFTR* mutation class, and sex, as appropriate, will be included in the Comparator Cohort in the study analyses in each annual report. Each annual report will include the data collected during the previous calendar year. Longitudinal analyses will be included in the final report. The

Historical Cohort will provide an estimate of rates for variables supporting Objectives 1 and 2 and be included in the first yearly report.

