9.5 Study Size

The number of patients included in annual analyses will be dependent on the use of ivacaftor amongst patients in the registries. Ivacaftor is indicated for the treatment of CF in patients 6 years of age and older who have a *G551D* mutation in the *CFTR* gene. The estimated prevalence of the *G551D* mutation is approximately 2374 patients globally. Based on 2010 data, the CF Trust has enrolled 432 patients with the *G551D* mutation and the CF Foundation has enrolled 1035 patients with the *G551D* mutation.^{1,2} By working with these patient registries, we expect to be able to analyse more than half of the *G551D* patients in the world. Assuming that most *G551D* patients are indicated for treatment with ivacaftor and will receive treatment, the number of patients analysed is expected to be sufficient to achieve the objectives of the study.

The power to detect a difference in death rates between the Ivacaftor Cohort and the Comparator Cohort are presented in the table below. The death rate in the unexposed group, 103 of 9385 (0.011), was obtained from the 2010 UK Trust Annual Report and is shown below as Proportion 1. Proportion 2, the death rate in the Ivacaftor Cohort, is varied between 138 in 10,000 (0.0138) to 440 in 10,000 (0.0440).

Table 6 Power Calculations for Detecting Differences in Death Rates

Relative Risk	Proportion 1	Proportion 2	Alpha	Power (N Exposed = 432 ^a)	Power (N Exposed = 1035 ^b)
1.25	0.011	0.0138	0.1	0.111	0.180
1.5	0.011	0.0165	0.1	0.190	0.347
1.75	0.011	0.0193	0.1	0.287	0.534
2	0.011	0.0220	0.1	0.393	0.703
2.25	0.011	0.0248	0.1	0.501	0.829
2.5	0.011	0.0275	0.1	0.604	0.911
2.75	0.011	0.0303	0.1	0.695	0.958
3	0.011	0.0330	0.1	0.772	0.981
3.25	0.011	0.0358	0.1	0.834	0.992
3.5	0.011	0.0385	0.1	0.882	0.997
3.75	0.011	0.0413	0.1	0.919	0.999
4	0.011	0.0440	0.1	0.945	1.000

Note: Power is from a single-sided Fisher exact test of 2 proportions, with alpha = 0.1, assuming equal N per group (Ivacaftor Cohort and Comparator Cohort). Because the number of patients exposed is based on the "best-case scenario" (i.e., all eligible patients receiving ivacaftor), the power is likely higher than actual.

^a CF Trust

^b CF Foundation

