Another limitation of the observational study design is differential follow-up of the patient cohorts, which can introduce ascertainment bias of outcomes. To minimise this bias, the CF patient registries collect comprehensive data at least annually on all patients enrolled. To identify whether ascertainment bias is introduced into the study, cohorts will be compared for healthcare utilisation including CF care visits and hospitalisations.

Additionally, because eligibility for a cohort is determined each year, a patient may be included in different cohorts over the course of this study. This would limit the ability to include this patient in longitudinal evaluations, such as for change in lung function over time.

Limitations of study setting

The analysis of CF disease progression will be limited to CF lung disease severity and clinical signs of CF disease progression, based on definitions accepted in the medical community. Although the change in lung function over time will be analysed, the analysis is limited by differences in the frequency of data collection for pulmonary function testing. Pulmonary function test results are collected in both the CF Trust and the CF Foundation patient registries. However, the CF Trust database collects pulmonary function test results at the annual encounter only, whilst the CF Foundation allows CF care providers to enter pulmonary function test results for all patient encounters throughout the year. In either case, data are collected only if available. Additionally, the CF Trust collects only the best pulmonary function test result (newly implemented in 2012), whereas the CF Foundation collects the actual result at each encounter.

Whilst the patient registries do not provide the precision of a clinical study where all patients have pulmonary function testing at a defined and frequent interval, the available pulmonary function test data will be used to define CF lung disease severity (see Section 9.3) and provides a qualitatively accurate measurement of CF disease progression amenable to annual reporting. Given the variability in the number of data points available for each patient, analysis of the change in lung function over time utilising registry data is likely underpowered to detect differences between the Ivacaftor and Comparator Cohorts.

Limitations of the use of a Historical Cohort

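### The interventional-study exclusion looks at the same year in which outcomes are counted; this inflates the retained death rate and can bias the cohort comparison if participation differs

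*Protocol*

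**What the plan says.** Protocol Sections 9.1.2.1 to 9.1.2.6 give all six cohorts one and the same exclusion criterion: "Participation in an interventional study during the analysis period (if available". The abstract repeats it.

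The length of the period is fixed for the annual safety analysis. Section 9.2.5 explains the choice of a single year for the Historical Cohort: "A 1-year window was selected to match the window for safety outcome analysis in the Ivacaftor and Comparator Cohorts". Section 9.9 adds that "because eligibility for a cohort is determined each year, a patient may be included in different cohorts over the course of this study". Section 9.2.6 states that "Longitudinal analyses will be included in the final report", without saying what the analysis period is for those analyses.

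Nothing in these sections separates patients already in a study on the first day of the year from those who enter later. No censoring at study entry is stated. The limitations in Section 9.9 cover selection bias, differential follow-up, the Historical Cohort and power, but not this exclusion. No participation rate is given for any cohort.

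**The concern.** A cohort should be defined by what is known when follow-up starts. Here membership also depends on what happens during follow-up. For death the consequence is mechanical. Someone who dies in March cannot enter a study in October and is kept with the death. Someone who enters in October is removed with nine months of survival. Deaths stay in while survivors leave, so the proportion dying among those retained is too high.

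The comparison between cohorts is at stake if the excess is not equal on both sides. Section 9.3.4 plans crude relative risks or risk differences with confidence intervals, and adjustment only where the data allow. Adjustment would not restore the discarded person-time. Comparators differ from ivacaftor users in genotype and, by definition, have never taken ivacaftor, so equal participation in interventional studies cannot be taken for granted.

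**Working it through.** **Inputs from the protocol (Section 9.5).** "The death rate in the unexposed group, 103 of 9385 (0.011), was obtained from the 2010 UK Trust Annual Report"; 103/9385 = 0.01097. For numbers exposed, "the CF Trust has enrolled 432 patients with the *G551D* mutation and the CF Foundation has enrolled 1035 patients". For Table 6, "Power is from a single-sided Fisher exact test of 2 proportions, with alpha = 0.1, assuming equal N per group".

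**The plan's own figure.** Exact one-sided Fisher power at alpha 0.1 with equal groups, at relative risk 2 (0.011 v 0.022), is 0.386 for 432 per group (Table 6: 0.393) and 0.706 for 1035 per group (Table 6: 0.703). All 24 entries of Table 6 reproduce within two percentage points, so 0.011 is used below as the annual death risk.

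**Assumptions not in the protocol.** A fraction q of patients would enter a study during the year, at a time spread evenly over it, with the same hazard as everyone else.

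**Effect on the retained death risk.**
- Hazard: h = −ln(1 − 0.011) = 0.01106.
- Chance that a would-be entrant dies before entry: Pd = 1 − 0.011/0.01106 = 0.0055.
- Retained risk = [(1 − q) × 0.011 + q × Pd] / [(1 − q) + q × Pd].
- For q = 10%: (0.00990 + 0.00055) / (0.90 + 0.00055) = 0.0116, a ratio of 1.055 to the true 0.0110.

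| Joining in the year (assumed) | Retained death risk | Ratio to 0.0110 |
|---|---|---|
| 2% | 0.0111 | 1.01 |
| 5% | 0.0113 | 1.03 |
| 10% | 0.0116 | 1.06 |
| 20% | 0.0124 | 1.12 |

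A simulation of 20 million patients at q = 20% gave 0.0124, in agreement.

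**Effect on the relative risk when the truth is 1.00** (ivacaftor v comparator participation, equal hazards)

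| Participation | Observed relative risk |
|---|---|
| 5% v 5% | 1.00 |
| 2% v 10% | 0.96 |
| 10% v 2% | 1.04 |
| 5% v 20% | 0.91 |
| 20% v 5% | 1.10 |

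**Does censoring cure it?** In the same simulation at q = 20%, counting joiners up to study entry gave 0.01108 deaths per person-year against a true 0.01106. The timing error disappears.

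**If joiners are healthier.** Let joiners have k times the risk of the others, with the others' relative risk set to h′ = 1/(pk + 1 − p), where p is the fraction joining.
- Under exclusion the ratio is (1 − 0.5pkh′)/(1 − p). With k = 0.5 this is 1.082 at p = 10% and 1.015 at p = 2%, so the relative risk reads 1.015/1.082 = 0.94.
- Under censoring the ratio is (1 − p + 0.5pk)h′/(1 − 0.5p), which gives 1.025 and 1.005, so the relative risk reads 0.98.

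Censoring removes most of this distortion, but not all.

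**Other outcomes.** Hospitalisations, exacerbations and complications can happen before study entry without preventing it. The rule then removes events as well as time, and the sign of any error depends on how those events relate to enrolment, which the protocol does not describe.

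**The case against.** Several points against the concern are sound.

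- The criterion is identical in every cohort. With equal participation and equal risk the relative risk is unaffected. A reader might infer that the rule makes ivacaftor look safer; without participation rates the documents support neither that direction nor its opposite.
- Participation also covers patients already in a study when the year starts. Excluding those is an ordinary baseline restriction. If half of a 10% participation were of this kind, the joiners would be 5/95 = 5.3% of the rest and the excess about (1 − 0.026)/(1 − 0.053) = 1.03, not 1.06.
- A reader might infer that one study in any year removes a patient from all longitudinal analyses. At 5% to 10% yearly participation in independent years that would be 1 − 0.95^5 = 23% to 1 − 0.90^5 = 41% of patients. The text does not say this: eligibility is decided each year (Section 9.9), the safety window is one year, and the lung-function analysis in Section 9.3.4.4 does not mention the exclusion. The term is merely undefined for longitudinal use.
- The 0.94 above mixes the timing error with healthier joiners, so it should not be read as the effect of the rule alone.
- The study is descriptive, and Section 9.9 speaks of detecting 2- to 3-fold differences. At 0.011, the expected deaths are about 432 × 0.011 = 5 and 1035 × 0.011 = 11 a year. A shift of 4% to 5% in the relative risk is small beside that.
- The registries are secondary sources, and the criterion itself is conditional on availability. Enrolment dates may not exist, and the exclusion plausibly keeps investigational treatment out of the cohorts.

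These points limit the size and reach of the concern. They do not remove the defect in the death rate, which follows from the eligibility rule as written.

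**Conclusion.** The concern holds in a limited form. The exclusion uses information from after the start of follow-up, and any mid-year joining inflates the retained annual death rate: by about 3%, 6% and 12% at 5%, 10% and 20% joining. These figures assume equal risk, evenly spread entry and that all participants enter during the year. Bias in the Ivacaftor versus Comparator relative risk is conditional on unequal participation or unequal joiner risk. At participation up to 10% it is about 4% to 5% in either direction for death with equal joiner risk. For the non-fatal outcomes no direction can be given. The effect is modest, but the limitations section does not mention it and it is cheap to avoid.

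**What to change.** - In Sections 9.1.2.1, 9.1.2.2, 9.1.2.4 and 9.1.2.5, and in 9.1.2.3 for consistency, exclude only patients who are in an interventional study at the start of each annual period.
- Where an enrolment date is available, count later entrants' events and person-time up to study entry and censor there.
- Where a registry holds only a yearly flag, keep the present exclusion for the main analysis and add a sensitivity analysis that retains patients not flagged in the previous year.
- Report participation by cohort in each annual report, and add the point to Section 9.9.
- State in Section 9.2.6 that for longitudinal analyses the criterion is applied year by year and not over the whole study.

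The cost is protocol wording, a censoring date and a little extra analysis by the registries. Some informative censoring remains if joiners are healthier. The yearly-flag sensitivity analysis will include some time on investigational treatment, which is why it should not be the main analysis.

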9.1.2.3 Historical Cohort

Inclusion Criteria

1. Patients with CF in the CF Trust or the CF Foundation patient registries
2. Patients with the *G551D-CFTR* mutation
3. Patients with no evidence of ivacaftor exposure before ivacaftor was available commercially

Exclusion Criterion

1. Participation in an interventional study during the analysis period (if available)

9.1.2.4 Ivacaftor Pregnancy Study Cohort

Inclusion Criteria

1. Female patients with CF in the CF Trust or the CF Foundation patient registries
2. Patients 13 years of age or older
3. Patients treated with ivacaftor

Exclusion Criterion

1. Participation in an interventional study during the analysis period (if available)

9.1.2.5 Comparator Pregnancy Study Cohort

Inclusion Criteria

1. Female patients with CF in the CF Trust or the CF Foundation patient registries
2. Patients 13 years of age or older
3. Patients with no evidence of ivacaftor exposure (current or past)
4. Patients matched on *CFTR* genotype class to patients in the Ivacaftor Pregnancy Study Cohort

Exclusion Criterion

1. Participation in an interventional study during the analysis period (if available)

9.1.2.6 Drug Utilisation Cohort

Inclusion Criteria

1. Patients with CF in the CF Trust or the CF Foundation patient registries
2. Patients with current ivacaftor exposure

Exclusion Criterion

1. Participation in an interventional study during the analysis period (if available)

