9.2.3 Study Cohorts

Patients from the patient registries will be categorised into 6 cohorts.

1. The Ivacaftor Cohort will include all ivacaftor-treated patients enrolled in the CF Trust or CF Foundation patient registries, regardless of age, *CFTR* genotype, or pulmonary function.

2. The Comparator Cohort will include patients who are not receiving and have never received ivacaftor and are a match on age group, *CFTR* genotype class, and sex to patients in the Ivacaftor Cohort. Based on the mechanism of action of ivacaftor and the availability of genetic testing, it is expected that most patients with *G551D-CFTR* mutation will be exposed to ivacaftor during the study period, making it challenging to identify a comparator cohort of patients with CF with the *G551D-CFTR* mutation who are not exposed to ivacaftor. Therefore, patients in the Comparator Cohort will be matched on *CFTR* genotype class based on the functional classification of *CFTR* alleles.^{14,22}
3. The Historical Cohort will include patients who have the *G551D-CFTR* mutation, were enrolled in the patient registries in 2008 (before ivacaftor was available in clinical studies and commercially in the UK and the US), and have no evidence of exposure to ivacaftor.
4. The Ivacaftor Pregnancy Study Cohort will include all female patients 13 years of age or older who were enrolled in the patient registries and were treated with ivacaftor.
5. The Comparator Pregnancy Study Cohort will include female patients who are not receiving and have never received ivacaftor and are a match on *CFTR* genotype class to patients in the Ivacaftor Pregnancy Cohort.
6. The Drug Utilisation Cohort will include all patients who were enrolled in the patient registries with evidence of ivacaftor exposure.

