9.3.1 Variables for Cystic Fibrosis Trust Patient Registry (UK)

9.3.1.1 Exposure

Ivacaftor exposure will be determined by first evidence of ivacaftor treatment and patients will remain exposed until there is evidence of discontinuation of ivacaftor in the patient registry database. Because start and stop dates are available, ivacaftor exposure will be calculated in days. When start and stop dates are not available due to missing data, algorithms will be used to extrapolate duration of exposure based on timing of patient encounters and drug exposure data available. The exposure algorithm includes the following rules: if only month and year are available, then the assumed start or stop date will be the 15th of the month, or if only year is available, then the assumed start or stop date will be June 30th. Ivacaftor exposure will be categorised into the meaningful groups based on the distribution of exposure, such as <1 year, 1 to <2 years, and ≥2 years. For patients who discontinue treatment with ivacaftor, reason for discontinuation (lack of benefit, side effect, other) will be described.

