2. To evaluate the outcomes of pregnancy in ivacaftor-treated patients	UK, US	Ivacaftor Pregnancy Study; Comparator Pregnancy Study; Historical	
 Comparison of pregnancy outcomes between the Ivacaftor Pregnancy Study Cohort (ivacaftor-treated patients) and the Comparator Pregnancy Study Cohort (concurrent nonexposed patients) Descriptive statistics for the Historical Cohort (historical nonexposed patients) will be available for comparison to the Ivacaftor Pregnancy Study Cohort (ivacaftor-treated patients). Comparisons to be based on 95% confidence intervals.
3. To evaluate the drug utilisation of ivacaftor	UK, US	Drug Utilisation	All ivacaftor-treated patients will be included in the drug utilisation analysis. No comparisons will be made.
4. To evaluate CF disease progression in ivacaftor-treated patients	UK, US	Ivacaftor Comparator	
 Comparison of CF disease progression between the Ivacaftor Cohort (ivacaftor-treated patients) and the Comparator Cohort (concurrent nonexposed patients)

CF: cystic fibrosis; UK: United Kingdom; US: United States.

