16.2 Drug Utilisation Subprotocol

The drug utilisation subprotocol will be conducted using the same Drug Utilisation Cohort definition (Section 9.1.2.6), analysis variables (Section 9.3.2.3), and statistical analysis (Section 9.3.4.3), as specified in the main protocol for Objective 3 (drug utilisation).

To meet the subprotocol objective, data for outcomes will be analysed separately for each registry starting at Year 2 of the main protocol. All enrolled patients exposed to ivacaftor will be included in the Drug Utilisation Cohort. Ivacaftor exposure will be derived as described for the CF Trust (Section 9.3.1.1) if start and stop dates of ivacaftor treatment are available, or as described for the CF Foundation (Section 9.3.2.1) if start and stop dates of ivacaftor treatment are not available.

Drug utilisation of ivacaftor will be described by the frequency of ivacaftor exposure, by *CFTR* genotype class, age, sex, and percent predicted FEV₁. Because ivacaftor was not available in Ireland and France until 2013, data for drug utilisation analyses will not be available for Vertex until 2014; therefore, data will be analysed separately for each registry for 4 years. The milestones for the annual reports are provided in Table 8.

Table 8 Subprotocol Study Milestones

Milestone ^a	Planned Dates	
	Ireland	France
Start of data collection ^b	May 2014 ^c	May 2014 ^c
End of data collection ^b	May 2017	May 2017
Year 1 Report	not applicable	not applicable
Year 2 Report	October 2014	October 2014
Year 3 Report	October 2015	October 2015
Year 4 Report	October 2016	October 2016
Registration in EU PAS Register ^d	tbd	tbd
Final report of study results	October 2017	October 2017

CF: cystic fibrosis; EU PAS: European Union Post-authorisation Study; tbd: to be determined.

^a Milestones are based on the main protocol (i.e., the Year 1 Report is relative to the start of data collection for the CF Trust [UK] and CF Foundation [US] registries).

^b Per EU Good Pharmacovigilance Practices VIII.B.2, the start and end of data collection for secondary use of data are when the analytical datasets are available.

^c Because ivacaftor was not commercially available until 2013, data for drug utilisation analyses will not be available for extraction until 2014. Therefore, subprotocol reports will begin with the Year 2 (relative to the main protocol).

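### The protocol says all ivacaftor-treated patients enter the drug utilisation analysis, but the cohort criteria drop anyone recorded in any interventional study that year, which lowers the annual user counts

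*Protocol*

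**What the plan says.** Three places in the Protocol define the drug utilisation population with no exception:

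- 9.1.1 Study Population: "The Drug Utilisation Cohort will include all patients who have ever been treated with ivacaftor".
- 9.2.3 Study Cohorts: "The Drug Utilisation Cohort will include all patients who were enrolled in the patient registries with evidence of ivacaftor exposure". The study design part of the abstract says the same.
- 9.3.4, Table 5, Objective 3: "All ivacaftor-treated patients will be included in the drug utilisation analysis". The same cell states that no comparison is made.

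The formal criteria in 9.1.2.6 are narrower in two ways. The inclusion criterion is "Patients with current ivacaftor exposure", and the exclusion criterion is "Participation in an interventional study during the analysis period (if available". The study population part of the abstract repeats the exclusion.

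The drug utilisation subprotocol (16.2) adopts the 9.1.2.6 definition and then states: "All enrolled patients exposed to ivacaftor will be included in the Drug Utilisation Cohort".

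The analysis itself (9.3.4.3) is the frequency of exposure by genotype class, age, sex and percent predicted FEV1. The secondary objectives (8.2.3) are off-label use in children under 6, in non-G551D Class III patients and in non-Class III patients.

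**The concern.** Each registry runs its own analysis. An analyst who follows Table 5 counts every exposed patient; one who follows 9.1.2.6 leaves out those known to be in a study. The protocol does not say which table is intended.

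The exclusion also fits this objective less well than the others. In the cohorts that are compared, it limits contamination by trial treatments. Objective 3 compares nothing, and its output is how many patients take the drug and who they are. The criterion is not limited to ivacaftor studies or to study-supplied drug. A patient on commercial ivacaftor who enrols in, say, an inhaled antibiotic trial is a real user, yet is left out of that year's count. The objective includes off-label subgroups that may be small, where a few unreported removals can matter.

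**Working it through.** **No planned figure to reproduce.** The protocol gives no expected number of users and no trial-participation share, so the check is mainly a comparison of text.

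**Step 1: the definitions side by side (all Protocol).**

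| Place | Exposure required | Study participants |
|---|---|---|
| 9.1.1 | ever treated | not excluded |
| 9.2.3 | evidence of exposure | not excluded |
| 9.3.4, Table 5 | treated | not excluded |
| 9.1.2.6 | current exposure | excluded where known |
| Abstract, study population | current evidence of exposure | excluded where known |
| 16.2 | exposed, using the 9.1.2.6 definition | as 9.1.2.6 |

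The first three rows conflict with the next two. Section 16.2 imports 9.1.2.6, so it is not independent evidence of the conflict, but it carries the criterion to Ireland and France.

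**Step 2: direction of the effect.** Let N be the exposed patients in a registry in a year and f the share of them recorded as being in an interventional study. The reported count is N × (1 − f), so the loss is N × f. It is never negative, and it is zero where participation is not recorded. Table 4 lists no trial-participation variable for either registry, so f may depend on what each registry happens to capture in each year.

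**Step 3: illustration of size.** Inputs: N = 432 (UK) and 1035 (US), the 2010 G551D counts in 9.5, taken as all treated. The note to Table 6 calls this a best case. The share f is not in the protocol; 2% to 20% is an assumption.

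| f | UK: 432 × f | US: 1035 × f | Total: 1467 × f |
|---|---|---|---|
| 2% | 8.6 | 20.7 | 29 |
| 5% | 21.6 | 51.8 | 73 |
| 10% | 43.2 | 103.5 | 147 |
| 15% | 64.8 | 155.3 | 220 |
| 20% | 86.4 | 207.0 | 293 |

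These numbers do not separate ivacaftor trials from unrelated ones, so they are not counts of lost commercial users. They also leave out off-label users without G551D.

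**Step 4: what happens to one patient over time.** Section 9.9 notes that "because eligibility for a cohort is determined each year, a patient may be included in different cohorts over the course of this study". Take a hypothetical UK patient on commercial ivacaftor from 2013 onwards who is in an unrelated trial in 2014. If the trial is recorded, the patient is counted for 2013, left out for 2014 and counted again for 2015. The 2014 count is one lower although use has not changed. The exposure record is unaffected: under 9.3.1.1, "patients will remain exposed until there is evidence of discontinuation of ivacaftor in the patient registry database". In the US (9.3.2.1), a stop requires a completed medications form without ivacaftor. Leaving a year's cohort sets no stop date under either rule.

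**The case against.** **'All' may mean all who meet the criteria.** The protocol uses the same pattern for the Ivacaftor Cohort: inclusive wording in 9.1.1 and 9.2.3, then the same exclusion in 9.1.2.1. On that reading 9.1.2.6 governs and there is no real conflict. This is plausible for the summary descriptions, but no passage says so. Table 5 sits in the statistical section and states what the analysis includes. The passages still need reconciling.

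**The exclusion has a purpose here.** This stands. A reader might infer that it does nothing except remove real users. It does more: a patient given ivacaftor in a trial outside the label would otherwise appear among the off-label users in 8.2.3. The US exposure variable in Table 4 is yes (150 mg or other) or no, and the UK variable is start and stop with reason. Neither shows who supplied the drug, so the exclusion is the only stated safeguard against that misreading. Simply deleting it would be wrong.

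**Differences between registries matter little.** This stands in part. The registries are analysed separately and Objective 3 makes no formal comparison. Counts from successive annual reports will still be read together, and a change in what is recorded could look like a change in use.

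**Conclusion.** The concern holds in a limited form. The descriptive statements and the formal criteria disagree on who is counted. Where the exclusion is applied, it lowers the annual user counts, including commercial users in trials unrelated to ivacaftor. The amount cannot be calculated from the protocol and may vary by registry and year. The figures under Step 3 of the working rest on an assumed participation share and on every G551D patient being treated; they show scale only.

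Two stronger readings are not supported. A reader might infer that patients will appear to stop and restart treatment. They will not: exposure comes from registry treatment records, and 9.3.4.3 lists no discontinuation, restart or persistence measure. A reader might also infer that the age, FEV1 or off-label distributions are distorted. That is possible if study participants differ from other users, but nothing in the protocol shows it.

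This is an inexpensive improvement to Objective 3. It does not affect the safety, pregnancy or disease progression analyses.

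**What to change.** For the Drug Utilisation Cohort only:

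1. Remove the interventional-study exclusion from 9.1.2.6 and from the abstract. Section 16.2 follows automatically because it refers to 9.1.2.6.
2. Report all exposed patients, with those recorded as being in an interventional study in a separate row.
3. Give the off-label subgroup counts with and without that row, so that study-supplied use is not read as off-label prescribing.
4. State for each registry and year whether study participation was available.
5. In the same edit, reconcile ever treated (9.1.1) with current exposure (9.1.2.6). The first gives a cumulative count and the second an annual one.

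Leave the criterion in the safety and pregnancy cohorts.

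The cost is one deleted criterion, one added table row, a second set of off-label counts and a few sentences of text. No information is lost, because the counts under the present rule are still obtained by leaving out the separate row. The downside is that where participation or supply source is not recorded, some study-supplied use stays unseparated. That already happens under the present wording.
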